The University of Texas Southwestern Medical Center at Dallas Institutional Review Board

PROJECT SUMMARY

Principal Investigator:

[name], PT, DPT, PhD

Study Title:

Scoliosis-Specific Exercises for At-Risk Mild AIS Curves: A Multi-Site Preliminary Randomized Trial

Sponsor/Funding Source:

Scoliosis Research Society

Purpose:

To investigate the feasibility and short-term effectiveness of scoliosis specific exercises as part of a multi-center randomized controlled trial in patients with mild AIS curves at the greatest risk of progression. Specifically, our study aims are as follows:

Aim 1: The primary aim is to assess the feasibility of a multi-site prospective randomized controlled trial in skeletally immature patients with mild AIS curves at high risk of progression. Participants instructed in scoliosis-specific exercises (SSE) provided by physical therapists certified in the Schroth-based method (SSE group) will be compared to the standard-of-care of observation (control group).

Feasibility will be evaluated according to participant:

1) recruitment rate at each site (measured by the number of participants enrolled per month at each site)

2) overall recruitment rate (measured by the total number of participants enrolled after 1 vear)

3) treatment attendance in the SSE group (measured by the percentage of prescribed hours of physical therapy sessions attended)

4) home exercise adherence in the SSE group according to weekly e-mails (measured by the percentage of prescribed exercises completed from baseline to 1 year)

5) home exercise adherence in the SSE group according to a smartphone application (measured by the percentage of prescribed exercises completed from baseline to 1 vear)

6) home exercise adherence in the SSE group according to an exercise log (measured by the percentage of prescribed exercises completed from baseline to 1 year)

Aim 2: The secondary aim is to assess whether scoliosis-specific exercises (SSE) will be more effective in skeletally immature patients with mild AIS curves at high risk of progression, Current Protocol 4.19.2019.docx

Page 1 of 13

compared to the standard-of-care of observation (control).

The outcome quantifying the effect of 1 year of physical therapy intervention will include:

1) curve magnitude (measured by the Cobb angle on radiograph at baseline and 1 year)

2) curve progression (measured by whether the curve progresses >5° after 1 year)

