lacking. Given the persisting uncertainty among medical professionals regarding the true potential of SSE, the purpose of this trial is to objectively and rigorously evaluate SSE compared to observation (standard-of-care). The results from this trial will provide much needed high-quality evidence regarding the feasibility and efficacy of SSE. In particular, this study will limit the inclusion criteria to skeletally immature patients with mild AIS curves. These patients are at highest risk of curve progression and have a greater potential for a meaningful effect with early intervention before their growth spurt and curve acceleration phase. Many families hope to avoid the need for bracewear.⁸ A smaller curve is more flexible²⁸ and may be more amenable to changes from exercise, especially before spinal growth is complete. In particular, mechanical wedging of the immature disc and vertebral body may still be reversible.²⁹

Concise Summary of Project:

This study will be a multi-center, dual-arm randomized control study evaluating skeletally immature patients with mild AIS curves. At six institutions, patients will be randomized into either the scoliosis-specific exercise (SSE) treatment arm or a control group. The SSE group will receive training in SSE, posture, and activities of daily living by physical therapists certified in Schroth-based exercise methods. The control group will not receive SSE instruction and will only be observed by their treating orthopaedic surgeon (which is considered the standard-of-care treatment method). Results will be compared after one year of treatment.

Study Procedures:

All patients with AIS meeting the following inclusion criteria will be eligible to participate in this trial: diagnosis of AIS; ages 10 to 17 years; major curve Cobb angles 12° to 24°; thoracolumbar, lumbar, or primary thoracic curve patterns; and Risser grade 0. Patients will be excluded according to the following exclusion criteria: scoliosis other than AIS, upper thoracic or double curve patterns, developmental disorders that prevent understanding and compliance with an exercise schedule, current or previous brace wear, and previous participation in a SSE program, previous spine surgery, inability to commit to performing a home exercise program for 15 minutes a day, 5 days a week, and inability to commit to attend at least 8 hours of PT within 6 months.

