Patients randomized to the exercise group who never initiate physical therapy (do not attend even one session of physical therapy or begin a home exercise program) may be switched to the control group and observed in the same manner.

3) Outcome measures

Patients and their legal guardians will be asked to fill-out three self-reported outcome scores at their initial appointment and 1 year post the initiation of their participant in the study. The questionnaires to be completed include:

SRS-22:

The survey is a valid instrument for the assessment of the health related quality of life of patients treated for idiopathic scoliosis. This Heath Related Quality of Life (HRQL) questionnaire is designed to assess the effect that idiopathic scoliosis has on the patient in regards to pain, activity level, medications used, and satisfaction with treatment to date, and mental health status. The SRS-22 is one of the frequently tested scoliosis questionnaires and has been shown to have high levels of both reliability and validity.

Patient and parent survey:

A 3 question survey (one for patient, one for parent) that asks patients and parents questions regarding their/the child's attitudes toward SSE, their/their child's posture, and their/their child's scoliosis.

Once all measurements have been collected at the patient's enrollment at and one year follow-up, patients in this group will continue to be tracked through observation until skeletal maturity in order to record whether the patient experienced curve progression, was prescribed a braced, or proceeded to surgical treatment.

Current Protocol 4.19.2019.docx Page 6 of 13 While the SSE training will be considered for research purposes only, all regularly scheduled clinic visits with the patients' treating physicians and x-rays will be considered standard-of-care.

Anticipated Results:

We predict that at one-year follow-up:

I. A multi-site prospective randomized controlled trial in skeletally immature participants with mild AIS curves at high risk of progression is feasible as evidenced by acceptable participant recruitment rates (\geq 18 participants per site after 1 year), treatment attendance (\geq 80%), and home exercise adherence.

II. Scoliosis-specific exercises will be effective and will demonstrate:

- 1) Significantly smaller change in curve magnitude
- 2) Significantly reduced incidence of curve progression
- 3) Significantly reduced incidence of brace prescription

Criteria for Inclusion of Subjects:

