Eligible patients will be screened based on the research coordinator's review of the scoliosis clinics at TSRH or from the recommendation of the patient's treating physician. The Investigators in this study will have the ability to suggest their own patients. Once deemed eligible, a member of the study team will meet with the patient and his or her legal guardians in order to review the consent form. The patient and family will be given ample time to review the consent form and ask any questions. In order to respect the privacy of potential patients, all consenting procedures will occur in a private clinic exam room. The research coordinator will explain to the family that their participation in the study is voluntarily and they will receive their participation (or lack of) in the study will not affect their standard treatment or relationship with their treating physician. Appropriate patient assent and caregiver consent will be obtained by a member of the study team prior to any study activities occurring (per IRB protocol) Patients meeting the study criteria who consent to participate will be randomly assigned to either the treatment or control arm in a 2:1 ratio. Patients will be assigned a group using a block-randomized, within site method. Patient assignment will be done by utilizing a computer-generated list and pre-sealed envelopes that will be distributed to the participating sites before enrollment. The list and envelopes will be generated by the statistician at Texas Scottish Rite Hospital.

If an eligible patient is missed in clinic whom the research team has an existing relationship with through a medical staff member on the study team, they may be contacted by a member of the research team via phone. The patient family will be identified and then told the following:

Schroth Ex-Trial Phone Solicitation Script:

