I am a [researcher or physical therapist] from Scottish Rite Hospital for Children. I'm calling you because I wanted to tell you about an opportunity to participate in a study that is looking at what happens to small curves and whether physical therapy exercises can slow the progression of the curve. Patients in this study are assigned randomly, like a flip of a coin, to one of two groups: a group that does exercises and a group that does not do exercises but only receives standard observation by the physician. You have twice the chance of being assigned to the exercise group. The group that does exercises is asked to do exercises 15 minutes a day, 5 days per week for one year. If you decide to participate, whether you are ^{Current Protocol 4.19.2019.docx} Page 9 of 13

assigned to the exercises group or the observation group, there is a \$200 stipend paid to you at the end of one year. You can choose to stop participating for any reason at any time, and this will not affect the way you are treated. We will also keep your health information confidential. Does this sound like something you are interested in getting more information about at your next visit?

If the family and patient are interested in participating in the study, the patient and family will be invited to return to the hospital for consent. The patient will then be consented according to the format listed above and be given ample time for questions and review. If the patient is not interested in participating in the study, they will be thanked for their time and a note will be made in the research documents that the patient declined participation.

Potential Risks:

Identifiable risks associated with participation in this study would be a potential loss of confidentiality and tired or sore muscles from the exercises.

Subject Safety and Data Monitoring

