All information obtained through medical and radiographic records will be reviewed solely by the primary investigators, co-investigators, and other study team personnel. Publically reported information will be in the form of a statistical summary only: no information will be divulged that could be linked to a specific patient involved with the study. No patient information will be disclosed outside of the study team. The University of Texas Southwestern Medical Center Institutional Review Board may review the research information for auditing purposes. The team will keep the consents and study files in both a locked cabinet as well as electronic copies within the electronic study folder (this folder will be stored on password encrypted hard drive which may be accessed by members of the study team only). All other electronic data collected will be stored on a password protected electronic database with access limited to the study team.

Procedures to Maintain Confidentiality:

All normally used means for protecting patient confidentiality will be strictly followed. All consents, clinical and radiographic measurements, and patient demographics will be stored in a secure electronic database. This database will be password protected and access will be limited to only individuals on the study team. Data will be de-identified for each patient by assigning a Study ID in the database. All PHI and the unique study ID for each patient will be stored in a separate password-protected and encrypted spreadsheet that only members of the study team at TSRH will have access to. Only a statistical summary of the information will be published: at no time will any data published include information that can be linked to a study participant. All requirements for HIPAA compliance in regards to patient confidentiality will be followed and the University of Texas Southwestern Medical Center's Institutional Review Board will have the right to inspect all medical records related to this study for the purpose of ensuring patient confidentiality.

Current Protocol 4.19.2019.docx Page 10 of 13

Biostatistics

Continuous variables will be summarized with means, standard deviations and ranges and analyzed using student t-tests; categorical variables will be summarized as counts and percentages and analyzed using Fischer's exact tests. Data will be checked for normality and equal variance.

Potential Benefits:

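### With 2:1 allocation, pooled t-tests and an equal-variance check that leads nowhere, the Cobb comparison is exposed to unequal spread; naming Welch's test in advance settles it cheaply (minor point, secondary aim)

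*Combined protocol and SAP*

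**What the plan says.** The Biostatistics section gives the whole analysis of continuous outcomes in one clause: "Continuous variables will be summarized with means, standard deviations and ranges and analyzed using student t-tests". It follows with "Data will be checked for normality and equal variance". It states no method or threshold for the check and no action if it fails. It names no unequal-variance test.

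Under Recruitment Methods and Consenting Process, patients are "randomly assigned to either the treatment or control arm in a 2:1 ratio", and "Patients will be assigned a group using a block-randomized, within site method". The telephone script confirms which arm is larger: "You have twice the chance of being assigned to the exercise group".

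The continuous efficacy outcome, listed under Aim 2 in the Purpose section, is "curve magnitude (measured by the Cobb angle on radiograph at baseline and 1 year"). Aim 2 is the secondary aim; the primary aim is feasibility. The documents give no SD, alpha, power or total sample size.

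**The concern.** Student's t-test pools the two sample variances, weighting each by its degrees of freedom. With equal arms, the pooled standard error is right on average even when the spreads differ. With 2:1 arms it is not, because the larger arm dominates the pooled variance while the smaller arm dominates the true variance of the difference. If the smaller (control) arm is more variable, the test rejects too often and its interval is too narrow. If the larger (SSE) arm is more variable, the test is conservative and loses power.

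Either direction is conceivable. Effective exercises could leave the control arm as the wider mix of stable and progressing curves. Variable adherence could instead widen the SSE arm. The check does not settle the matter as written, since it has no consequence: either the pooled test stands whatever the check shows, or the test is chosen after the data are seen. At stake are the p-value for Cobb change and any interval reported with it, which a later, larger trial might rely on.

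**Working it through.** **Inputs from the documents.** Pooled t-test and a check without consequence (Biostatistics). 2:1 allocation, SSE larger (Recruitment Methods). Feasibility threshold of at least "18 participants per site after 1 year" (Anticipated Results). Six sites: "At six institutions, patients will be randomized into either the scoliosis-specific exercise (SSE) treatment arm or a control group" (Concise Summary of Project).

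**Derived size.** 6 × 18 = 108, which at 2:1 is 72 SSE and 36 control. This comes from a feasibility threshold and is not a planned sample size, so sizes down to 24:12 were also run.

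**Assumptions.** Two-sided 5%; normal data except in the mixture below; SD ratios of 1.25 and 1.5 in both directions. The plan has no figure of its own to reproduce.

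**Step 1: large-sample error of the pooled test.** Let k² = [pooled variance × (1/n₁ + 1/n₂)] / [σ₁²/n₁ + σ₂²/n₂]. The actual error is 2 × (1 − Φ(1.96k)). Here n₁ = 72 (SSE), n₂ = 36 (control) and 1/72 + 1/36 = 0.04167.

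- Control SD 1.25, SSE SD 1: pooled variance (71 + 35 × 1.5625)/106 = 1.1857. Numerator 0.04941, denominator 1/72 + 1.5625/36 = 0.05729. k = 0.929, error **6.9%**.
- Control SD 1.5, SSE SD 1: pooled variance (71 + 35 × 2.25)/106 = 1.4127. Numerator 0.05886, denominator 0.07639. k = 0.878, error **8.5%**.
- SSE SD 1.25, control SD 1: pooled variance 1.3768. Numerator 0.05737, denominator 0.04948. k = 1.077, error **3.5%**.
- SSE SD 1.5, control SD 1: pooled variance 1.8373. Numerator 0.07655, denominator 0.05903. k = 1.139, error **2.6%**.

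With n₁ = n₂ the numerator equals the denominator, so k = 1. The unequal allocation is what drives the error.

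**Step 2: simulation** (100,000 trials per row). The switching rule uses Welch if a 5% variance test rejects and Student otherwise. Paired figures are for the Brown-Forsythe and F tests.

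| n (SSE:control) | More variable arm, SD ratio | Student | Welch | Switching rule | Check rejects |
|---|---|---|---|---|---|
| 72:36 | control, 1.25 | 6.8% | 5.0% | 6.0 / 5.8% | 28 / 35% |
| 72:36 | control, 1.5 | 8.5% | 5.0% | 5.7 / 5.4% | 71 / 80% |
| 72:36 | SSE, 1.25 | 3.6% | 5.1% | 4.3 / 4.4% | 26 / 30% |
| 72:36 | SSE, 1.5 | 2.6% | 5.0% | 4.6 / 4.7% | 69 / 77% |
| 24:12 | control, 1.25 | 6.7% | 5.0% | 6.4 / 6.2% | 10 / 15% |
| 24:12 | control, 1.5 | 8.6% | 5.1% | 7.4 / 6.8% | 25 / 37% |

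Independent runs differ by 0.1 to 0.2 points.

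**Step 3: what prevention of progression would do.** Model the change in each arm as a mixture: stable curves N(0, 3²) and progressors N(10, 3²), in degrees. The arm SD is then √(9 + 100p(1 − p)), where p is the proportion progressing. For controls, p = 38% or 50%, two of the rates in the Background. For SSE, p = 10% or 15% (assumed). The arm SDs are:

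- control: √32.56 = 5.71 (38%) or √34 = 5.83 (50%);
- SSE: √18 = 4.24 (10%) or √21.75 = 4.66 (15%).

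The SD ratio is 1.22 to 1.37. Simulated at 72:36, the pooled 95% interval covers 92.2 to 93.3% and Welch's about 95%. With a smaller effect (38% against 25 to 30%) the ratio is 1.04 to 1.08 and pooled coverage 94.3 to 94.7%. With equal progression in both arms, Student rejects in 4.9 to 5.0% of trials.

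**Step 4: cost and gain of Welch.** With equal SDs, at a difference giving about 80% power, Welch against Student is 78.8% against 79.2% at 72:36 and 76.2% against 77.7% at 24:12. If the SSE SD is 1.5 times the control SD at 72:36, Welch has 79.0% power and Student 70.5%.

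**The case against.** **Nothing in the documents shows that the arms will differ in spread.** This stands. The SD ratios, the mixture's 10-degree shift and the SSE progression rates are assumptions. The Background rates carry no one-year time frame, and the 50% rate refers to progression of at least 5 degrees.

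**A reader might infer that the trial's own hypothesis implies a false-positive rate of 7 to 8.5%.** It does not. Preventing progression creates unequal spread only together with a difference in means; under no effect the arms share one distribution and Student holds its level. The inflated error needs equal means with unequal SDs, for example exercises that help some patients and harm others. The prevention argument supports only a loss of interval coverage, and Biostatistics does not itself promise an interval.

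**The direction may be the reverse.** The Background's one-year cohort comparison reports 23.5% improved and 11.8% worsened with specific exercises, against 11.1% and 13.9% with non-specific exercise. With assumed shifts of 5 to 10 degrees and noise SD 3, the control-to-SSE SD ratio is 0.89 to 0.93, which makes Student mildly conservative. That comparator was not observation, so this is indicative only. It shows that the sign is unknown, which favours a test that is valid either way.

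**A check of equal variance beside a t-test naturally means switching tests.** That is a fair reading, so one cannot say that the check would fail to help. At 72:36 and ratio 1.5 a switch brings 8.5% down to 5.4 to 5.7%. But the plan states no switch, and at 24:12 a switch leaves 6.2 to 7.4%.

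**Welch loses power in the mixture** (72.9% against 78.8% for 38% against 10% progressors). That gap reflects the pooled interval being too narrow, with 92.4% coverage, so it is not a real advantage of Student.

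**Conclusion.** The point holds as a minor, conditional one. The plan pairs a pooled t-test with 2:1 allocation and a variance check without consequence. If the spreads differ by a factor of 1.25 to 1.5, the error at 72:36 is about 7 to 8.5% or about 3.6 to 2.6%, depending on which arm is more variable. If SSE reduces progression, the harm is an interval covering about 92 to 94%, and close to 95% if the effect is modest.

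Three stronger readings are not supported: that the arms are bound to differ in spread, that the check could not help, and that Welch is free. The figures rest on a sample size derived from a feasibility threshold, assumed SD ratios and a 5% level the plan does not state. The outcome serves the secondary aim of a preliminary trial, so this does not threaten the trial's main purpose.

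**What to change.** In Biostatistics, replace the Student t-test and the equal-variance check with a sentence such as: *Continuous outcomes will be compared between arms with the Welch (unequal-variance) t-test and reported with its 95% confidence interval; no preliminary test of equal variance will be used to choose the test.*

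This needs no new data and no change to conduct. If the spreads are in fact equal, the interval is about 0.5% wider at 72:36 and 1.8% wider at 24:12, with the power loss shown in Step 4 (0.4 and 1.5 points). In return the test holds its level whichever arm is more variable, and a choice that could otherwise be made after seeing the data is removed.

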Managing AIS can be considered a quality-of-life issue, since it does not result in premature death.³ Scoliosis may be associated with pain, torso deformity, psychological distress and pulmonary dysfunction.⁴ Bracing may result in decreased guality-of-life such as reduced activity and self-image, especially those with smaller curves.⁵ Patients commonly report discomfort with wearing a brace. Furthermore, most patients prescribed brace wear are not compliant.⁶ In contrast to bracing, exercise for AIS has been found to be emotionally satisfying⁷ and is the patient-preferred option.⁸ Furthermore, supervised Schroth exercises for AIS have been shown to significantly improve self-image according to the SRS-22 as compared to a control group.⁹ However, in North America, exercises are typically not offered to patients with smaller curves as part of the medical management of AIS. Exercise treatment during adolescence may prevent curve progression and its consequences, as less than 10% of curves kept below 29° at maturity continue to progress into adulthood.¹ At skeletal maturity, only 30% of curves greater than 30° continue progressing slowly, but 70% of the curves >50° progress at a rate of 1° per year.¹⁰ The negative consequences of progressive scoliosis most commonly manifest themselves once curves exceed 40-50°, justifying efforts to prevent progression.^{1,4} Furthermore, patients who are Risser 0 with mild curves are at a high risk of curve progression.¹¹ In a sample of 123 AIS patients with curves 10-49°, Bunnell (1986) reported a 68% risk of curve progression $\geq 10^{\circ}$ in patients who are Risser 0, and a 44% risk of curve progression ≥10° in patients with curves <20°.¹¹ In a sample of 727 JIS and AIS patients with curves 5-29°, Lonstein & Carlson (1984) reported a 38% risk of curve progression $\geq 10^{\circ}$ in patients who are Risser 0, and a 38% risk of curve progression $\geq 10^{\circ}$ in patients with curves <20° who are Risser 0-1.12 In a large cohort (sample size unknown) of AIS patients who are Risser 0 and 1, a 50% risk of curve progression ≥5° was found in patients with curves 15-30°.¹³

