Recent, growing evidence supports the role of SSE methods to treat AIS. Systematic reviews (SR) conclude that exercises may be effective in reducing curve progression and reducing brace prescription.^{14,19} The evidence guality in the aforementioned reviews is low, with only one randomized controlled trial (RCT) included. Many of the studies are retrospective and most lack controls. Since the most recent SR, two recently published RCTs found SSE effective in reducing curve progression. One RCT of SSE consisted of SEAS (Scientific Exercise Approach to Scoliosis) in mild AIS compared to PT exercises that were not scoliosis-specific.²¹ A significantly improved Cobb angle in the SSE group was found immediately after treatment (at skeletal maturity) and at 1 year of follow-up post-treatment.²¹ The second RCT compared three groups of patients with AIS curves 10-60°: a supervised outpatient Schroth group, unsupervised home exercise Schroth group and a control group.²² At 24-weeks of follow-up, the Cobb angle improved in the supervised Schroth group but worsened in the other 2 groups.²² Another prospective controlled cohort study of SSE (Scientific Exercises Approach to Scoliosis) in mild AIS curves reported that brace prescription and curve progression were both significantly reduced compared to PT exercises that were not scoliosis-specific after 1 year of follow-up.²⁷ Brace prescription in patients was 6.1% in the SSE group compared to 25.0% in the non-SSE group. Curves improved in 23.5% and worsened in 11.8% of the SSE group compared to the non-specific exercise group in which 11.1% improved and 13.9% worsened.²⁷ Furthermore, a study of SSE (Schroth method) in children with idiopathic scoliosis reported significantly reduced curve progression in patients receiving intensive scoliosis in-patient rehabilitation compared to untreated patients.²⁴ Another study of the Schroth method described 50 patients with AIS treated on an out-patient basis for 4 hours a day, 5 days a week, for 6 weeks, followed by continued therapy at home. The average Cobb angle decreased from 26.1° pre-treatment to 23.5° at 6 weeks, 19.3° at 6 months, and 17.9° at 1 year.²⁵

The clinical management of patients with mild scoliosis remains controversial. Although various conservative strategies have been proposed, there is no consensus in the literature on the optimal treatment. High-quality evidence for the Schroth-based method is Current Protocol 4.19.2019.docx

Page 3 of 13

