All patients diagnosed with Adolescent Idiopathic Scoliosis who meet the following inclusion criteria will be eligible to participate in this trial:

- 1) Age 10 to 17 years
- 2) Major curve Cobb angles of 12° to 24°
- 3) Compensatory curve should be less than 5° of the main curve (ex: 10° if the main curve is 15° or 15° if the main curve is 20°)
- 3) Risser Grade 0
- 4) Single thoracic, thoracolumbar, or lumbar curve patterns

Criteria for Exclusion of Subjects:

Patients will be excluded according to the following exclusion criteria:

- 1) Scoliosis other than AIS (congenital, neuromuscular, etc)
- 2) Upper thoracic or double curve patterns
- 3) Diagnosis of a developmental disorder that prevents understanding and compliance with an exercise schedule
- 4) Current or previous brace wear
- 5) Previous participation in a SSE program
- 6) Previous spine surgery
- 7) Patient inability to commit to attend at least 8 hours of PT within 6 months

Sources of Research Material:

Current Protocol 4.19.2019.docx Page 7 of 13 After the consenting process, patient demographics will be collected from the patient chart. All demographic information, clinical, and radiographic measurements will be recorded after informed consent is obtained during the patient's appointments.

Texas Scottish Rite Hospital will serve as the lead institution for this study and will create/maintain a REDCap database to house all study data. All other participating sites will obtain IRB approval from their own institutions and will enter into a Data Use Agreement contract with Texas Scottish Rite Hospital in order to access the database and run data analysis. Only a limited data set will be shared between the institutions, and all patient information will be entered into the database in a de-identified fashion. The data to be shared between institutions includes:

- Patient study number (to be generated for each institution in a de-identified format through REDCap)
- Date patient is consented to the study
- Date physical therapy/control status is initiated
- Age
- Initial curve Cobb angles
- Risser sign
- De-identified x-ray images (AP and Lateral views)
- Height, Weight, and BMI
- Physical activity level
- Curve pattern (classification as thoracic, thoracolumbar, or lumbar)
- Schroth curve pattern
- Trunk rotation
- Triradiate status
- Menarchal status
- SRS-22
- 3 question parent survey about attitudes toward SSE, posture, and scoliosis

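### The planned t-tests and Fisher's tests use neither site nor a model of baseline Cobb angle: a modest, cheaply avoided loss of precision on secondary outcomes, clearest for brace prescription

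*Combined protocol and SAP*

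**What the plan says.** The analysis plan is the short Biostatistics paragraph. Continuous variables are to be "analyzed using student t-tests; categorical variables will be summarized as counts and percentages and analyzed using Fischer's exact tests", and "Data will be checked for normality and equal variance". No covariate, site term, stratified test or regression is named anywhere, and no action is given if the variance check fails.

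The design supplies information that these tests leave unused:

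- **Site.** Recruitment Methods and Consenting Process: "Patients will be assigned a group using a block-randomized, within site method", with patients "randomly assigned to either the treatment or control arm in a 2:1 ratio". The Concise Summary gives six institutions.
- **Baseline.** Sources of Research Material lists "Initial curve Cobb angles" among the shared data. The inclusion criteria admit "Major curve Cobb angles of 12° to 24" (degrees), a twofold range.

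The three efficacy outcomes (Purpose, Aim 2) treat baseline differently. Curve magnitude is measured at baseline and 1 year, and Anticipated Results predicts a smaller change. Progression is a change of more than 5°. Both therefore subtract baseline. Brace prescription is a plain 1-year percentage.

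**The concern.** When randomisation is stratified by site, an analysis that omits site leaves between-site variation in the error term. When an outcome depends on a measured baseline variable, omitting that variable does the same.

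Brace prescription is the exposed outcome. The Background places bracing with moderate curves and observation with mild ones, so a child entering near 24° plausibly starts closer to a brace than one entering near 12°. Fisher's test treats the two as interchangeable.

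Anticipated Results predicts significant differences on all three outcomes, so these tests will be used for inference, possibly with only 36 controls. What is at stake is the width of intervals and some power on Aim 2. Aim 1 (recruitment, attendance, adherence) does not depend on these tests.

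**Working it through.** The plan gives no sample size, power, alpha, SD or effect size, so there is no figure of its own to reproduce.

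**Inputs from the documents.** Six sites; at least 18 participants per site (Anticipated Results, a feasibility criterion and not a powered size); 2:1 allocation. Hence 6 × 18 = 108, or 72 SSE and 36 control, 12:6 per site. Background, on a cited cohort: "Brace prescription in patients was 6.1% in the SSE group compared to 25.0% in the non-SSE group".

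**Assumptions.** Two-sided 5%. Entry Cobb uniform on 12° to 24°, so SD = 12/√12 = 3.46°. The cited brace rates serve only as planning values: that cohort's comparator was non-specific exercise, not observation.

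**1. Brace prescription.** Unadjusted SE of the risk difference:

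√(0.25 × 0.75/36 + 0.061 × 0.939/72) = √(0.005208 + 0.000796) = 0.077, or 7.7 points.

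For calculation only, bracing follows a cut-off on 1-year Cobb angle. The cut-off is solved so that each arm has its target rate; only the SD of change is then free. Matching both rates with one common cut-off implies the between-arm Cobb differences shown. Adjustment is linear regression on arm, baseline Cobb and site.

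| SD of change | Implied Cobb difference | Variance ratio, adjusted/unadjusted | Adjusted SE (points) |
|---|---|---|---|
| 4° | 4.5° | 0.83 | 7.0 |
| 6° | 6.0° | 0.90 | 7.3 |
| 8° | 7.6° | 0.95 | 7.6 |
| 12° | 10.9° | 0.98 | 7.6 |

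To see where any power gain comes from, Fisher's test is compared with re-randomisation within site under three adjustments (3,000 simulated trials per row, no site differences):

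| SD of change | Fisher | Site only | Site + pure noise covariate | Site + baseline Cobb |
|---|---|---|---|---|
| 4° | 74.5% | 74.2% | 79.2% | 83.9% |
| 6° | 73.9% | 73.8% | 78.6% | 81.6% |
| 8° | 73.6% | 73.2% | 77.9% | 80.9% |
| 12° | 73.7% | 73.2% | 78.2% | 79.1% |

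A meaningless continuous covariate adds about 5 points because it breaks ties in a discrete statistic and lets the test use its full 5%. At a common rate of 6.1% and SD 4° to 8°, Fisher's size is 2.7% to 3.0%; re-randomisation with baseline has 4.8% to 5.2%. Only the last column minus the noise column is baseline information: 4.7, 3.0, 3.0 and 0.9 points here, and about 1 to 8 points across repeated simulations. With large site differences (site SD 4°, SD of change 6°), an exact site-stratified test has 77.8% power against 75.4% for Fisher.

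**2. Cobb change.** With residual SD 5° (assumed), the baseline-only variance ratio of ANCOVA to the change-score t-test is 25/(25 + 12(1 − slope)²), where slope is that of 1-year on baseline Cobb:

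- slope 1: 25/25 = 1.00
- slope 0.8: 25/25.48 = 0.98
- slope 0.7: 25/26.08 = 0.96
- slope 0.5: 25/28 = 0.89

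Adding site gives a ratio of about 1 − ICC, or 0.90 at ICC 0.10. Power for an assumed 3° effect, t-test against ANCOVA with site: 83.5% vs 83.0% (slope 1, ICC 0) and 80.2% vs 82.7% (slope 0.7, ICC 0.05). The most favourable corner tried (slope 0.5, ICC 0.10) gives 76.3% vs 82.4%. The documents support no particular slope or ICC. The t-test's size is 5.1% at ICC 0 and 3.8% at ICC 0.10: conservative, not inflated.

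**3. Progression >5°.** The baseline-adjusted variance ratio is 1.01 (slope 1) and 0.98 (slope 0.7). For site, take a control risk of 50%, as the Background reports "a 50% risk of curve progression ≥5° was found in patients with curves 15-30" (degrees), and an assumed odds ratio of 1/3. Fisher against an exact site-stratified test: 68.6% vs 68.8% with equal sites, 67.0% vs 68.2% with site risks of 40% to 60%. Only an extreme spread of 25% to 75% gives more (58.3% vs 64.7%).

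**4. Unequal variances at 72:36.** With a control/SSE SD ratio of 0.67 to 1.5, Student's true size runs from 2.7% to 8.4%. Welch's stays at 4.9% to 5.1%.

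**The case against.** The case for leaving the plan alone is substantial. The tests are simple and, apart from Student's equal-variance assumption, valid. Efficacy is the secondary aim of a preliminary trial. Two of the three outcomes already subtract baseline and gain little. All of that stands, and it makes this an optional improvement.

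The brace figures also rest on a link that the documents do not supply: no threshold for bracing is given, and any discretion in prescribing would weaken the role of baseline. The planning rates imply Cobb differences of 4.5° to 10.9°, well above the 3° used for Cobb change; at such effects the planned t-test on change already has over 99% power. The two calculations are therefore separate illustrations and not one scenario. This limits how literally the brace ratios can be read, but not their direction.

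A reader might infer that the whole gap between Fisher and the adjusted test, up to about 10 points, is the price of ignoring site and baseline. It is not: about 5 points come from replacing a discrete, conservative test, and site alone adds nothing when sites do not differ.

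A reader might also infer that the t-test compares 1-year Cobb angles, which would cost more. Biostatistics does not say, but Anticipated Results points to change.

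**Conclusion.** The point holds as a modest loss of precision on Aim 2. For brace prescription the adjusted/unadjusted variance ratio is about 0.83 to 0.98, with about 1 to 8 power points from baseline. This assumes 72:36, the cited brace rates, a cut-off link from curve size to bracing, and an SD of change of 4° to 12°. For Cobb change, baseline and site each offer about 0 to 10% of variance, and nothing at slope 1 with no site differences. For progression >5° the gain is close to nil unless sites differ greatly.

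The stronger reading, that omitting site and baseline biases the results or inflates false positives, is not supported: randomisation protects the comparison, and site differences make the tests conservative. The one validity issue is separate: Student's size of about 3% to 8% when SDs differ by a factor of up to 1.5, with a planned check but no stated consequence. No feasibility conclusion changes.

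**What to change.** Optional rather than essential. Add to Biostatistics, before outcomes are examined:

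- Patients are analysed in the groups to which they were randomised. This needs saying because the Control Group section lets exercise-arm patients who never start be moved to control, and re-randomisation is valid only for groups as randomised.
- 1-year Cobb angle: ANCOVA with baseline Cobb angle and site, robust standard errors, adjusted mean difference with 95% CI.
- Brace prescription: risk difference adjusted for baseline Cobb angle and site by linear regression. The p-value comes from re-randomisation within site, following the actual block scheme, and it decides. A 95% CI with HC3 standard errors is descriptive. An HC2 Wald p-value should not be used, since it rejects in about 7% of null trials when braces are rare (about 6%).
- Progression >5°: may be stratified by site.
- Sensitivity analyses: Fisher's exact test, and any unadjusted t-test in Welch form.

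The cost is a few sentences, about 6 degrees of freedom and a short script; no new data. Cobb change may gain nothing. The brace p-value and its interval disagree on significance in about 10% to 11% of simulated trials at the cited rates (22% to 25% at half recruitment), so the text must say which decides.
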